1.1.5 RATIONALE FOR STUDY

NMES is hypothesised to improve neuropathy symptoms in people with DN by directly stimulating peripheral nerves and increasing circulation in the lower limbs. Findings from a proof-of-concept study of NMES in people with DN showed that Michigan Neuropathy Screening Instrument (MNSI) Part A questionnaire scores significantly improved from baseline after 10 weeks of daily NMES device use (p<0.028) (22). To further understand the effects of this intervention in people with DN, more high-quality research is needed.

Imperial College Healthcare

Research Governance and Integrity Team

Hence, this pilot, randomised, sham-controlled trial is planned to robustly assess the potential efficacy signal, feasibility and safety of a NMES device as an adjunct to standard of care in people with DN. The inclusion of a sham control also allows for the assessment of any sham treatment effects.

If this pilot RCT demonstrates a potential efficacy signal and the NMES device is deemed safe, future plans are to run a statistically powered, multi-centre, RCT. If clinical efficacy and safety are demonstrated in larger trials, this could lead to an accessible, non-invasive, safe and effective treatment option for patients with DN and may reduce the burden to patients and healthcare systems.

Details of the NMES device used in this study (Revitive Medic Coach, Actegy Ltd, Bracknell, UK) are described below in section **3.1 TREATMENT REGIMENS** and are described in the **Instructions For Use (IFU)** and **Investigator's Brochure (IB)**.

For further details on the justification of the trial please see the **Clinical Investigation Decision** document.

2. STUDY OBJECTIVES AND OUTCOME MEASURES

2.1 PRIMARY OBJECTIVES

The primary objectives are to assess the potential efficacy signal, feasibility and safety of a NMES device as an adjunct to standard of care in people with DN.

The potential efficacy signal of a NMES device as an adjunct to standard of care will be primarily assessed by a change in neuropathy symptoms from baseline to the end of the treatment phase (12 weeks), compared to a sham device as an adjunct to standard of care. Neuropathy symptoms will be measured using the MNSI and will also be evaluated at follow up 6 weeks and 26 weeks, but the end of the treatment phase (12 weeks) will be the primary timepoint of interest.

The feasibility of a NMES device as an adjunct to standard of care will be assessed through recruitment rate, which will compare number of patients pre-screened/identified and number of participants recruited at baseline, participant retention rate, which will compare number of participants randomised and number of participants on study at the end of the treatment phase (12 weeks) and follow up (26 weeks), and adherence to treatment at the end of the treatment phase (12 weeks), which will be measured through the Revitive App and a patient diary.

Imperial College Healthcare

Research Governance and Integrity Team

The safety of a NMES device as an adjunct to standard of care will be assessed through reporting of Adverse Events (AEs), Adverse Device Effects (ADEs), Serious Adverse Events (SAEs) and Serious Adverse Device Effects (SADEs). For further details of assessment of safety and definitions please see **7. ASSESSMENT OF SAFETY**.

2.2 SECONDARY OBJECTIVES

The secondary objectives are to determine if there are changes in other clinical and subjective outcomes when using a NMES device as an adjunct to standard of care in people with DN.

Other clinical and subjective outcomes include, but are not limited to, sural, superficial peroneal, common peroneal and tibial nerve conductivity, somatosensory nerve fibre function, mobility and balance, neuropathy signs and symptoms, protective sensation, neuropathic pain and device sensation. Changes in these outcomes from baseline to the end of the treatment phase (12 weeks) and follow up (26 weeks) will be compared to a sham device as an adjunct to standard of care. In addition, blood glucose will be compared from baseline to the end of the treatment phase (12 weeks). Participants' views on device credibility and expectancy will be compared after their first treatment session at baseline and their experiences of the study device will be compared at the end of the treatment phase (12 weeks).

2.3 PRIMARY OUTCOME MEASURE

The primary outcome is neuropathy symptoms measured using the MNSI Part A questionnaire at 12 weeks. The MNSI Part A is a validated screening questionnaire for DN, consisting of 15 yes or no questions about lower limb sensation. The total score is based on 13 questions, as two questions are excluded from the scoring (23,24).

2.4 PRIMARY OUTCOME MEASURE HYPOTHESES

Primary outcome null hypothesis (H₀): There is no statistically significant difference in change in neuropathy symptoms measured using the MNSI Part A questionnaire total score between the control and intervention groups from baseline to the end of the treatment phase (12 weeks).

Primary outcome alternative hypothesis (H₁): There is a statistically significant difference in change in neuropathy symptoms measured using the MNSI Part A questionnaire total score, between the control and intervention groups from baseline to the end of the treatment phase (12 weeks).

Research Governance and Integrity Team

2.5 FEASIBILITY OUTCOME MEASURES

- Recruitment rate measured using screening and randomisation logs
- Participant retention rate measured using randomisation and withdrawal logs
- Adherence to treatment measured using Revitive App and a patient diary

2.6 SAFETY OUTCOME MEASURES

- Adverse Events (AEs) collected and reported via AE form
- Adverse Device Effects (ADEs) collected and reported via AE form
- Serious Adverse Events (SAEs) collected and reported via SAE form
- Serious Adverse Device Effects (SADEs) collected and reported via SAE form

2.7 SECONDARY OUTCOME MEASURES

- Sural nerve conductivity measured using a nerve conduction study (NCS), includes conduction velocity (m/s), calculated using distance and latency (ms), and SNAP amplitude (μV) (central site only)
- Superficial peroneal nerve conductivity measured using a NCS, includes conduction velocity (m/s), calculated using distance and latency (ms), and SNAP amplitude (μV) (central site only)
- Common peroneal nerve conductivity measured using a NCS, includes conduction velocity (m/s), calculated using distance and distal latency (ms), Compound Muscle Action Potential (CMAP) amplitude (mV) and minimum F wave latency (ms) (central site only)
- Tibial nerve conductivity measured using a NCS, includes conduction velocity (m/s), calculated using distance and distal latency (ms), CMAP amplitude (mV) and minimum F wave latency (ms) (central site only)
- Somatosensory nerve fibre function measured using Quantitative Sensory Testing (QST) (central site only)
- Blood glucose measured using HbA1c
- Mobility and balance measured using validated Berg Balance Scale (BBS) (25)
- Neuropathy signs measured using the validated MNSI Part B physical examination (23,24)
- Protected sensation measured using monofilament test
- Symptoms measured using Total Symptom Score (TSS) covering paraesthesia, pain, numbness, cramp and sleep disruption on a 10point Numerical Rating Scale (NRS)
- Neuropathic pain measured using Neuropathic Pain Symptom Inventory (NPSI) (26)

Imperial College Healthcare

Research Governance and Integrity Team

- Device sensation measured using device sensory threshold and suprathreshold
- Device experience measured using device experience questionnaire
- Device credibility and expectancy measured using modified credibility and expectancy questionnaire (27)

Timepoints at which primary, feasibility, safety and secondary outcome measures are assessed are included in **Table 1**.

Table 1: Summary of objectives and outcomes

Objectives	Outcome measure	Measuring tool	Timepoint(s) of evaluation of this outcome
Primary objectives	Neuropathy symptoms (Primary)	MNSI Part A questionnaire	Week 6, Week 12 (Primary), Week 26
	Recruitment rate (Feasibility)	Screening logs and randomisation logs	Pre-screening / Identification, Recruitment and Consent, Baseline
	Participant retention rate (Feasibility)	Randomisation logs and withdrawal logs	Recruitment and Consent, Baseline, Week 12, Week 26
	Adherence to treatment (Feasibility)	Revitive App and a patient diary	Week 12
	Adverse Events (Safety)	AE form	Baseline, Week 3, Week 6, Week 9, Week 12, Week 26 (and any communication in between)

Imperial College Healthcare

	T	1 4 = 6	T
	Adverse Device	AE form	Baseline, Week
	Effects (Safety)		3, Week 6, Week
			9, Week 12,
			Week 26 (and
			any
			communication in
			between)
	Serious Adverse	SAE form	Baseline, Week
	Events (Safety)		3, Week 6, Week
			9, Week 12,
			Week 26 (and
			any
			communication in
			between)
	Serious Adverse	SAE form	Baseline, Week
	Device Effects		3, Week 6, Week
	(Safety)		9, Week 12,
			Week 26 (and
			any
			communication in
			between)
Secondary	Sural nerve conductivity	NCS	Week 12, Week
objectives	(Central site only)		26
	Superficial peroneal	NCS	Week 12, Week
	nerve conductivity		26
	(Central site only)		
	Common peroneal	NCS	Week 12, Week
	nerve conductivity		26
	(Central site only)		
	Tibial nerve	NCS	Week 12, Week
	conductivity (Central		26
	site only)		
	Somatosensory nerve	QST	Week 12, Week
	fibre function (Central		26
	site only)		
	Blood glucose	HbA1c	Week 12
	Mobility and balance	BBS	Week 12, Week
			26
	Neuropathy signs	MNSI Part B	Week 12, Week
		Questionnaire	26

Research Governance and Integrity Team

	Symptoms	TSS	Week 6, Week 12, Week 26
	Protected sensation	Monofilament test	Week 12, Week 26
	Neuropathic pain	NPSI	Week 12, Week 26
	Device sensation	Device sensory threshold and suprathreshold	Week 12, Week 26
	Device credibility and expectancy	Modified credibility and expectancy questionnaire	Baseline
	Device experience	Questionnaire	Week 12

3. STUDY DESIGN

3.1 TREATMENT REGIMENS

This is a multi-centre, double-blind, pilot, randomised (1:1), sham-controlled trial assessing two arms:

Arm 1 (Control group): Sham Device + Standard of

Care

Arm 2 (Intervention group): NMES Device + Standard of

care

3.1.1 STANDARD OF CARE

Standard of care is defined as the therapy for DN available locally to the clinical trial site. It can comprise of advice on glycaemic control, footcare, anticonvulsant and antidepressant medications. For pragmatism, standard of care will be as per local guidelines and is not standardised by the study protocol. A full medical and drug history will be taken at baseline and concomitant medications will be recorded and monitored at each study visit. There are no prohibited concomitant medications for this trial.

3.1.2 NEUROMUSCULAR ELECTRICAL STIMULATION DEVICE (INTERVENTION)

Revitive Medic Coach (Figure 2) is a CE Marked, Class IIa, NMES medical device. It is intended to deliver nerve and muscle stimulation of the legs, feet and ankles to actively improve circulation. It is suitable for healthy individuals or people with poor circulation, a sedentary lifestyle, limited mobility, following

Imperial College Healthcare

Research Governance and Integrity Team

surgery or injury and those with diabetes (including DN), osteoarthritis, peripheral arterial disease, chronic venous insufficiency and chronic obstructive pulmonary disease. The intended operator profile is based on users in the home environment.

The device causes nerve and muscle stimulation by applying electrical stimulation to the feet via large conductive rubber footpad electrodes. It is accompanied by a CE Marked Class II AC/DC power adaptor (Figure 2) for charging and once sufficiently charged can be cordless for use. Routinely, it is also accompanied with electrode body pads, but these will not be provided for this study. The device can be activated via the power on/off button on the device or by the Revitive App via Bluetooth pairing, which is available for download from Play or App stores. For the purposes of this study, participants will be provided with a study smartphone to access the Revitive App. The device includes hydration sensors, which provide feedback to the user if they are required to hydrate their feet to improve conductivity. It also has an IsoRocker function, which allows natural heel toe raises and accentuates the calf muscle pump action at the ankle.

The key device components that are intended to come into contact with the human body are the silicone rubber footplates. The device comes into non-invasive contact with the user's intact skin on the plantar surface, via the footplate electrodes. These are comprised of Silicone (ER-70 + Carbon Nanotube) rubber. Transient contact may also be made in carrying the device, plugging in the charging cables or in using the device display interface.

The device is programmed with the Standard Programme, constructed from 15 one-minute low frequency waveforms patterns that repeat twice in each 30-minute programme. The intensity of electrical stimulus can be varied from level 0 to 99. When first using the NMES device at the baseline visit, baseline device sensory and motor thresholds will be established for participants by systematically increasing the stimulation intensity in increments of one whilst the participant provides verbal sensory feedback. The minimal intensity, at which the participant is able to clearly feel electrical stimulation, will be recorded as the sensory threshold; and that producing visible muscle twitches of the medial gastrocnemius will be the motor threshold. The stimulation intensity will be adjusted to produce visible but non-painful contraction of the lower limb musculature at twice the individual motor threshold or as much as the participant can tolerate as comfortable (suprathreshold) and this will be recorded. Participants may not perceive any sensation or muscle contractions because of their diabetic neuropathy (a disease characterised by sensorimotor dysfunction). In this case, participants should be encouraged to use the device at the highest stimulation intensity (level 99), provided there

Imperial College Healthcare

Research Governance and Integrity Team

are no other concerns with using the device at this level. Device sensory threshold and suprathreshold will also be recorded at Week 12 and Week 26 to assess any change in participants' device sensation over time. At baseline, an IFU will be given to all participants so they can use their study device at home. At Week 3, Week 6 and Week 9 participants will be contacted to see how they are tolerating their study device. During this visit and across the treatment phase, the clinical judgement of the local Principal Investigator (PI) will determine whether a participant is experiencing problems that require reducing the stimulation intensity level or stopping treatment.

Further details on the NMES device can be found in in the **Instructions for Use (IFU)** and **Investigator's Brochure (IB)**.

[figure not shown]

Figure 2: Revitive Medic Coach and power adaptor

Imperial College Healthcare

Research Governance and Integrity Team

3.1.3 SHAM DEVICE (CONTROL)

A sham control device has been included for the assessment of any sham treatment effects. The sham device will be a modified Revitive Medic Coach with all external appearances the same but with a maximum voltage cap to provide only very low sensory stimulation. It will begin at an intensity level of 5 for the first minute then level 2 for the second minute, then to a level zero for the remaining session. The numbers on the sham device and the Revitive App will display at the corrected intensity, similar to the display units on the NMES device to prevent unblinding. As the sham device still produces some stimulation, albeit very low, it is possible that there may be a change in sural nerve conductivity in the control group.

The same procedure as for the intervention group will be followed in that participants will be familiarised with their allocated study device and be provided with a study smartphone. Device sensory and suprathresholds will be established at baseline and recorded at Week 12 and Week 26 to assess any change in participants' device sensation over time. Participants may not perceive any sensation or muscle contractions because the sham device produces very low stimulation and/or because of their diabetic neuropathy (a disease characterised by sensorimotor dysfunction). In this case, participants should be encouraged to use the device at the highest stimulation intensity (level 99), provided there are no other concerns with using the device at this level.

At baseline, an IFU will be given to all participants so they can use their study device at home. At Week 3, Week 6 and Week 9 participants will be contacted to see how they are tolerating their study device.

Further details on the sham device can be found in in the **Instructions for Use (IFU)** and **Investigator's Brochure (IB)**.

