8.2.4 SECONDARY OUTCOME MEASURES ANALYSIS

Secondary outcomes include, but are not limited to, sural, superficial peroneal, common peroneal and tibial nerve conductivity, somatosensory nerve fibre function, mobility and balance, quality of life, neuropathy signs and symptoms, protective sensation, neuropathic pain and device sensation. Secondary outcome measures will be analysed using appropriate statistical models with appropriate adjustments to investigate the difference in outcomes between the two treatment groups at baseline, 12 weeks and 26 weeks. Other outcomes such as device experience (patient questionnaire recorded at Week 12) will be summarised descriptively.

Intergroup comparisons of categorical variables will be analysed using chisquared test.

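### Device sensation is planned as a between-arm comparison, but levels recorded on the sham and on the active device do not share a scale of delivered stimulus

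*Protocol*

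**What the plan says.** - **Outcome.** Protocol 2.7 lists "Device sensation measured using device sensory threshold and suprathreshold".
- **Objective.** Protocol 2.2 closes its list of outcomes with "protective sensation, neuropathic pain and device sensation. Changes in these outcomes from baseline to the end of the treatment phase (12 weeks") and to Week 26, and says that these changes are compared with the sham arm.
- **Analysis.** Protocol 8.2.4 repeats the list, "protective sensation, neuropathic pain and device sensation. Secondary outcome measures will be analysed using appropriate statistical models", with the aim "to investigate the difference in outcomes between the two treatment groups at baseline, 12 weeks and 26 weeks". The next sentence has a separate descriptive class: "Other outcomes such as device experience (patient questionnaire recorded at Week 12) will be summarised descriptively".
- **Measurement.** Protocol 5.4 places randomisation before device set-up. The allocated device is then raised one level at a time. The sensory threshold is the lowest level clearly felt. The suprathreshold is a working level set from the motor threshold or from comfort. Section 3.1.2 gives the active device's stimulus intensity as 0 to 99.
- **Sham.** Protocol 3.1.3 describes a modified unit "with a maximum voltage cap to provide only very low sensory stimulation". Its output is described as a "level of 5 for the first minute then level 2 for the second minute, then to a level zero for the remaining session". Its numbers "will display at the corrected intensity, similar to the display units on the NMES device to prevent unblinding". Thresholds are established on it at baseline and recorded again at Weeks 12 and 26. Participants who feel nothing are encouraged to go to level 99, as in the active arm.

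**The concern.** A comparison of thresholds between groups needs one instrument, or two with a known conversion. Here the study device is both the treatment and the measuring instrument, and the sham was altered in the very property being measured. The level at which a sham participant first reports feeling something depends on what the sham delivers at that displayed level, as well as on the participant's nerves.

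At stake is how one secondary result is read. A gap between arms in threshold, or in change in threshold, could be reported as an effect on sensation when it comes from the construction of the sham. Equally, no gap could be reported as no effect.

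**Working it through.** The protocol gives no figure for this outcome, so there is none to reproduce. The check sets the passages side by side.

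**Step 1. What a recorded level means in each arm**

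| | Active (3.1.2, 5.4) | Sham (3.1.3, 5.4) |
|---|---|---|
| Range of the number | 0 to 99 | shown in similar units; level 99 is mentioned |
| Delivered stimulus | the level is the stimulus intensity | voltage-capped; described as 5, then 2, then zero |
| Link from number to stimulus | direct | not stated |
| Reasons given for feeling nothing (3.1.3, 3.3) | neuropathy | low sham output and/or neuropathy |

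The last row matters: the protocol itself names a device cause for feeling nothing, and that cause exists in one arm only.

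**Step 2. Possible meanings of the sham display**

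- The display runs like the active one whatever the output. The number then does not measure the stimulus.
- The display is a rescaled output. The same number then stands for different stimuli in the two arms.
- The display shows true output, at least up to the cap. Sham thresholds are then cut off at the cap, in that arm only, and a level of 99 is either unreachable or has no matching output.

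None of these gives a common scale over the full range.

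**Step 3. The timed 5/2/0 run**

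The protocol does not say whether it operates during threshold-finding. If it does, output falls while the operator raises the level. If it is suspended, the cap and the display question in Step 2 remain. The conclusion does not depend on which applies.

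**Step 4. What the contrast estimates**

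Let S be the stimulus that a participant needs. On the active device the recorded level is L = S. On the sham it is L = g(S), with g unknown. Then

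mean L(active) − mean L(sham) = [mean S(active) − mean S(sham)] − mean[g(S) − S] in the sham arm.

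The first bracket is the quantity of interest. The last term comes only from the device.

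- *At baseline*, randomisation makes the expected first bracket zero, so any systematic difference in level is the device term. Because the baseline level is taken on the allocated device after randomisation, it is not a common covariate, and adjusting for it does not remove the problem.
- *For change*, the active arm gives S(week 12) − S(baseline), and the sham arm gives g(S at week 12) − g(S at baseline). Wherever g is flat, the sham change is zero whatever happened to sensation. As an illustration, suppose a sham participant feels nothing at either visit and is recorded at 99 both times. The change is 99 − 99 = 0, which says nothing about nerve function. That 99 would be the value recorded is an assumption.

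**The case against.** The strongest objection is that the conversion may be known. Section 3.1.3 refers to the Instructions for Use and the Investigator's Brochure for further detail on the sham, and neither was seen. This stands in part. It limits the claim to what the protocol describes, and to what a difference *could* reflect. Even a documented conversion would have to be applied before any comparison, and the protocol does not mention one.

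Second, each participant is retested on the same device, so change is measured within device. That supports describing change within an arm, which is the purpose that 3.1.2 and 3.1.3 both give. It does not make the changes of the two arms comparable with each other.

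Third, the sentence in 3.1.3 about following the same procedure goes on to mention only familiarisation and the smartphone. That is correct, and it should not carry the argument. The following sentence in 3.1.3 establishes thresholds on the sham, and 5.4 describes a single stepwise procedure for all participants.

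Fourth, detailed secondary analyses are left to a statistical analysis plan that is not at hand. It can choose the model, but the contrast itself is already set in 2.2 and 8.2.4.

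Last, this is one secondary outcome of a pilot without a power calculation, and no stated decision rests on it. That stands and keeps the severity low.

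**Conclusion.** The point holds for the between-arm comparison of device sensation. As the protocol describes the two devices, recorded levels are not on a common scale of delivered stimulus, at baseline or at follow-up. A difference in level or change, or its absence, should not be interpreted as a difference in participants' sensation. Severity is minor to moderate: one secondary outcome is affected. Confidence is moderate, because the display-to-output mapping and the role of the timed run during threshold-finding are not in the protocol.

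Three stronger conclusions might be inferred, and the documents do not support them:

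- *That a stated share of the 0 to 99 scale lies beyond the sham's output.* The protocol does not say that the sham's 5 and 2 are in the active device's units, nor that level 5 equals the cap. Such a count would also not size any bias.
- *That most of the stepwise test on the sham is done at zero output.* Neither the pace of the steps nor whether the run operates at that point is stated.
- *That a visible twitch during set-up unblinds the outcome assessors.* Sections 3.2 and 5.4 require a blinded researcher for assessments. Nothing says that the staff who set up the device later score outcomes, or that the sham cannot produce a twitch, and no rate is given. No effect on the primary outcome is shown.

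**What to change.** 1. In 2.2 and 8.2.4, remove device sensation from the outcomes compared between arms and place it in the descriptive class that 8.2.4 already has. Possible wording: *Device sensation (sensory threshold and suprathreshold) will be summarised descriptively, separately by arm, as the level at each visit and the change from baseline. No between-arm test will be made, because levels recorded on the sham device do not measure delivered stimulus.* Keeping both arms respects the change-over-time purpose that 3.1.3 gives for the sham measurements.
2. Reconcile the threshold procedure in 3.1.2 and 5.4 with the sham description in 3.1.3. State what the displayed level means on the sham, and whether the timed run operates while thresholds are being found.

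**Cost.** A protocol amendment under 9.2, made before database lock. It adds no visits, forms or participant burden, and as an analysis change it can apply to all 64 planned participants. One secondary contrast is lost. The within-arm changes are uncontrolled, so they cannot separate a device effect from familiarity or retesting. Testing both arms with one calibrated stimulus would keep a valid contrast. It would need a new procedure, however, and could not recover baseline values already taken, since 3.5 dates the start of recruitment to August 2023.
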